5.7 Diet/Activity/Other Considerations

5.7.1 Diet

Subjects should maintain a normal diet unless modifications are required to manage an AE such as diarrhea, nausea or vomiting.

5.7.2 Contraception

Pembrolizumab may have adverse effects on a fetus in utero. Furthermore, it is not known if pembrolizumab has transient adverse effects on the composition of sperm.

For this trial, male subjects will be considered to be of non-reproductive potential if they have azoospermia (whether due to having had a vasectomy or due to an underlying medical condition).

Female subjects will be considered of non-reproductive potential if they are either:

- (1) postmenopausal (defined as at least 12 months with no menses without an alternative medical cause; in women < 45 years of age a high follicle stimulating hormone (FSH) level in the postmenopausal range may be used to confirm a post-menopausal state in women not using hormonal contraception or hormonal replacement therapy. In the absence of 12 months of amenorrhea, a single FSH measurement is insufficient.);

OR

- (2) have had a hysterectomy and/or bilateral oophorectomy, bilateral salpingectomy or bilateral tubal ligation/occlusion, at least 6 weeks prior to screening;

OR

- (3) has a congenital or acquired condition that prevents childbearing.

Female and male subjects of reproductive potential must agree to avoid becoming pregnant or impregnating a partner, respectively, while receiving study drug and for 120 days after the last dose of study drug by complying with one of the following:

- (1) practice abstinence[†] from heterosexual activity;

OR

- (2) use (or have their partner use) acceptable contraception during heterosexual activity.

Acceptable methods of contraception are[‡]:

Single method (one of the following is acceptable):

- intrauterine device (IUD)
- vasectomy of a female subject's male partner
- contraceptive rod implanted into the skin

Combination method (requires use of two of the following):

- diaphragm with spermicide (cannot be used in conjunction with cervical cap/spermicide)
- cervical cap with spermicide (nulliparous women only)
- contraceptive sponge (nulliparous women only)
- male condom or female condom (cannot be used together)

- hormonal contraceptive: oral contraceptive pill (estrogen/progestin pill or progestin-only pill), contraceptive skin patch, vaginal contraceptive ring, or subcutaneous contraceptive injection

†Abstinence (relative to heterosexual activity) can be used as the sole method of contraception if it is consistently employed as the subject's preferred and usual lifestyle and if considered acceptable by local regulatory agencies and ERCs/IRBs. Periodic abstinence (e.g., calendar, ovulation, sympto-thermal, post-ovulation methods, etc.) and withdrawal are not acceptable methods of contraception.

‡If a contraceptive method listed above is restricted by local regulations/guidelines, then it does not qualify as an acceptable method of contraception for subjects participating at sites in this country/region.

Subjects should be informed that taking the study medication may involve unknown risks to the fetus (unborn baby) if pregnancy were to occur during the study. In order to participate in the study subjects of childbearing potential must adhere to the contraception requirement (described above) from the day of study medication initiation (or 14 days prior to the initiation of study medication for oral contraception) throughout the study period up to 120 days after the last dose of trial therapy. If there is any question that a subject of childbearing potential will not reliably comply with the requirements for contraception, that subject should not be entered into the study.

5.7.3 Use in Pregnancy

If a subject inadvertently becomes pregnant while on treatment with pembrolizumab, the subject will immediately be removed from the study. The site will contact the subject at least monthly and document the subject's status until the pregnancy has been completed or terminated. The outcome of the pregnancy will be reported to the Sponsor and to Merck without delay and within 24 hours to the Sponsor and within 2 working days to Merck if the outcome is a serious adverse experience (e.g., death, abortion, congenital anomaly, or other disabling or life-threatening complication to the mother or newborn).

The study investigator will make every effort to obtain permission to follow the outcome of the pregnancy and report the condition of the fetus or newborn to the Sponsor. If a male subject impregnates his female partner the study personnel at the site must be informed immediately and the pregnancy reported to the Sponsor and to Merck and followed as described above and in Section 7.2.2.

5.7.4 Use in Nursing Women

It is unknown whether pembrolizumab is excreted in human milk. Since many drugs are excreted in human milk, and because of the potential for serious adverse reactions in the nursing infant, subjects who are breast-feeding are not eligible for enrollment.

5.8 Subject Withdrawal/Discontinuation Criteria

Subjects may withdraw consent at any time for any reason or be dropped from the trial at the discretion of the investigator should any untoward effect occur. In addition, a subject may be withdrawn by the investigator or the Sponsor if enrollment into the trial is inappropriate, the trial plan is violated, or for administrative and/or other safety reasons. Specific details regarding discontinuation or withdrawal are provided in Section 7.1.4 – Other Procedures.

A subject must be discontinued from the trial for any of the following reasons:

- The subject or legal representative (such as a parent or legal guardian) withdraws consent.
- Confirmed radiographic disease recurrence
- Unacceptable adverse experiences as described in Section 5.2.1.2
- Intercurrent illness that prevents further administration of treatment
- Investigator's decision to withdraw the subject
- The subject has a confirmed positive serum pregnancy test
- Noncompliance with trial treatment or procedure requirements
- The subject is lost to follow-up
- Administrative reasons

The End of Treatment and Follow-up visit procedures are listed in Section 6 (Protocol Flow Chart) and Section 7.1.5 (Visit Requirements). After the end of treatment, each subject will be followed for 30 days for adverse event monitoring (serious adverse events will be collected for 90 days after the end of treatment as described in Section 7.2.3.1). Subjects who discontinue for reasons other than recurrent disease will have post-treatment follow-up for disease status until disease recurrence, initiating a non-study cancer treatment, withdrawing consent or becoming lost to follow-up. After documented disease recurrence each subject will be followed by telephone for overall survival until death, withdrawal of consent, or the end of the study, whichever occurs first.

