2.0 TRIAL DESIGN

2.1 Trial Design

It is a single-arm phase II trial. The target population is patients with histologically diagnosed locally advanced ESCC patients (clinically staged at least T3 and/or any N and M0 by endoscopic ultrasonography [EUS] and fludeoxyglucose-positron emission tomography [FDG-PET]) who have received preoperative cisplatin-based chemoradiotherapy (CRT) followed by surgery, and exhibit high risk of tumor recurrence. Eligible patients will receive adjuvant cisplatin-based CRT followed by pembrolizumab for 18 cycles.

The study hypothesizes that adjuvant cisplatin-based CRT followed by pembrolizumab will improve the 1-year relapse-free survival rate for these high-risk ESCC patients from 32% to 60%. With the two-sided type 1 error probability of 0.05 and type 2 error probability of 0.2, the study needs to enroll a total of 26 patients, taking another 10% of dropout rate. The duration of patient accrual is expected as 24 months. To detect the mature overall survival data, additional follow-up period of 36 months is needed.

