7.1.1.5.3 Subsequent Anti-Cancer Therapy Status

The investigator or qualified designee will review all new anti-neoplastic therapy initiated after the last dose of trial treatment. If a subject initiates a new anti-cancer therapy within 30 days after the last dose of trial treatment, the 30 days Safety Follow-up visit must occur before the first dose of the new therapy. Once new anti-cancer therapy has been initiated the subject will move into survival follow-up.

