7.1.5.5 Follow-up Visits

Subjects who discontinue trial treatment for a reason other than disease progression will move into the Follow-Up Phase. Every effort should be made to collect information regarding disease status until the start of new anti-neoplastic therapy, disease progression, death, end of the study or if the subject begins retreatment with pembrolizumab as detailed in Section 7.1.5.5. Information regarding post-study anti-neoplastic treatment will be collected if new treatment is initiated.

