8.2 Statistical Analysis Plan

8.2.1 Sample Size Determination

According to the subgroup analysis of our previous study [12], the median RFS for locally advanced ESCC patients who have received preoperative cisplatin-based CRT followed by surgery, and exhibit high risk of tumor recurrence (defined as closed or involved margin [$\leq 1\text{mm}$] or ENI or ypN2-3) is 6.7 months, equivalent to a 1-year RFS rate of 32.3%. It would need a sample size of 24 patients to detect a difference of the 1-year RFS rate from 32% to 60% by calculated using an exact binomial test with a power of 80% and a 5% significance level. Having taken an additional 10% of early drop-out rate into consideration, the total enrolled patient number will be 26 for this study. We estimate an enrollment rate of 12 patients per year at my center. Therefore, total study period will be 5 years, including 2 years of patient enrollment and 3 years of patient follow-up.

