8.2.2 Definition of Variables

8.2.2.1 Recurrence-free survival is the time from enrollment to disease recurrence or the last follow-up (censored). Recurrence is defined by suspicious lesion noted by tumor imaging according to RECIST 1.1. Tissue proof for suspicious lesion is recommended if it is feasible.

8.2.2.2 Overall survival is the time from enrollment to death of any cause or the last follow-up (censored).

8.2.2.3 Evaluation of Toxicity: The incidence and severity of toxicity will be summarized according to the NCI Common Toxicity Criteria Version 4.0.

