8.2.3 General Statistical Consideration

8.2.3.1 All statistical analyses will be performed for intent-to-treatment population.

8.2.3.2 The survival estimates will be derived from Kaplan and Meier curves.

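### Recurrence is no longer tracked once a patient starts non-study cancer therapy, so 1-year RFS can be biased, most plausibly upward

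*Combined protocol and SAP*

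**What the plan says.** Disease-status follow-up for patients who stop trial treatment without recurrence is described in Section 5.8: "Subjects who discontinue for reasons other than recurrent disease will have post-treatment follow-up for disease status until disease recurrence, initiating a non-study cancer treatment". Withdrawal of consent and loss to follow-up are the other end points. Section 1.0 (Duration of Participation) has the same list. Section 7.1.5.5 limits collection in the same way: "Every effort should be made to collect information regarding disease status until the start of new anti-neoplastic therapy". Section 7.1.1.5.3 adds: "Once new anti-cancer therapy has been initiated the subject will move into survival follow-up". Section 6.1 (footnote b) and Section 7.1.5.5.1 describe what is left: a telephone contact every 12 weeks about survival status. None of these places asks for recurrence status after new therapy has begun.

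On the analysis side, Section 8.2.2.1 defines the endpoint: "Recurrence-free survival is the time from enrollment to disease recurrence or the last follow-up (censored". Death is not listed as an RFS event, and new anti-cancer therapy is not mentioned. Section 8.2.3 states: "All statistical analyses will be performed for intent-to-treatment population", with Kaplan-Meier estimation. Section 10.6 rules out imputation.

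**The concern.** A patient who stops trial treatment for toxicity, or by the investigator's decision, and is then given other cancer therapy before a recurrence is recorded stays in the analysis set, but the primary outcome is no longer measured. A recurrence two months later has no route into the database. Because death is not an RFS event, the survival call does not recover it: the patient can die of the disease and still be censored as recurrence-free.

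Kaplan-Meier treats censored patients as having the same later risk as those still followed. If new therapy is started because relapse is suspected, that is wrong, and the estimate is too high. The trial has one arm and compares its result with a fixed historical rate, so there is no concurrent control in which such an error could partly cancel. The 1-year RFS rate is the primary endpoint. The median and 3-year RFS rest on the same curve.

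**Working it through.** **1. The plan's own figure.** Section 2.1 sets the error rates: "With the two-sided type 1 error probability of 0.05 and type 2 error probability of 0.2". Section 8.2.1 names an "exact binomial test with a power of 80% and a 5% significance level" and a target "to detect a difference of the 1-year RFS rate from 32% to 60" per cent, and arrives at 24 patients, 26 with drop-out. With n = 24, a null rate of 0.32 and at most 0.025 in the upper tail, the smallest critical count is 13: P(X ≥ 13 | 0.32) = 0.0202 and P(X ≥ 13 | 0.60) = 0.787. That is within 2 points of the stated 80%, so the sample size reproduces closely and is not in dispute. The critical count is derived here; the plan states none.

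**2. Can new therapy precede recorded recurrence?** Yes. Section 5.8 lists several reasons for stopping other than recurrence. Section 5.5.2 removes from the trial patients who need non-protocol cancer therapy during treatment, and prohibits nothing in post-treatment follow-up. On-treatment imaging comes every 4 cycles of 3 weeks, so 12 weeks apart.

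**3. Which starts matter for the primary endpoint?** Only those before month 12. Section 1.0 plans about 56 weeks of treatment, so these are patients who stop early. Later starts affect 3-year RFS.

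**4. Size of the Kaplan-Meier bias.** The documents give neither the number of such patients nor their risk. Assumptions:

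- constant recurrence hazard, with 1-year RFS of p (0.32 or 0.60) in patients who do not start new therapy;
- a share f (10% or 20%) of those at risk at month 6 starts new therapy without recurrence and is censored there;
- their later hazard is m times that of the others.

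RFS at month 6 is p^(1/2). From month 6 to 12, the others remain recurrence-free with probability p^(1/2) and the affected patients with probability p^(m/2). So:

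- Kaplan-Meier estimates p;
- true rate = (1 − f)·p + f·p^((1+m)/2);
- bias = f·[p − p^((1+m)/2)].

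Example: p = 0.32, f = 0.10, m = 2. Then 0.32^1.5 = 0.181, and the bias is 0.10 × (0.320 − 0.181) = 0.014, or +1.4 points.

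| p | f | m = 0.5 | m = 1 | m = 2 | m = 3 |
|---|---|---|---|---|---|
| 0.32 | 10% | −1.1 | 0 | +1.4 | +2.2 |
| 0.32 | 20% | −2.1 | 0 | +2.8 | +4.4 |
| 0.60 | 10% | −0.8 | 0 | +1.4 | +2.4 |
| 0.60 | 20% | −1.6 | 0 | +2.7 | +4.8 |

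(Bias in percentage points of 1-year RFS.)

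**5. What the shares mean in patients.** At p = 0.32, 26 × 0.32^(1/2) = 14.7 patients are at risk at month 6, so 10–20% is 1.5 to 2.9 patients. At p = 0.60, 26 × 0.60^(1/2) = 20.1 are at risk, so 2.0 to 4.0 patients.

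**6. The binomial test.** Section 8.2.1 does not say how a patient censored before month 12 is scored. In a simple proportion, changing one patient from success to failure moves the rate by 1/26 = 3.8 points (1/24 = 4.2).

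**The case against.** The strongest reply is that the gap is narrow. Section 8.2.2.1 accepts a suspicious lesion on imaging as recurrence and only recommends tissue proof, so a patient treated because of such a lesion may already have had an event. Imaging of symptomatic regions (Section 6.1, footnote e) and unscheduled procedures (Section 7.1) are allowed. Non-protocol cancer therapy is prohibited during treatment, which covers the 12-month window. The censoring rules behind the historical 32.3% are not given; if they were similar, part of any bias would be shared. All of this stands and limits the likely number of patients. It does not close the gap for therapy started without a suspicious lesion on imaging.

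Several stronger readings are tempting but not supported:

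- *RFS is certainly biased upward.* No passage says why new therapy would be started. The bias is zero if the start is unrelated to risk, and slightly negative if later hazard falls.
- *The bias is much larger.* If every affected patient would recur by month 12, it tends to f·p: 3.2 to 6.4 points at 32% and 6.0 to 12.0 at 60%. That is a limiting case, with nothing in the documents behind it.
- *The false-positive rate is inflated by a known amount.* The plan gives no critical count and no scoring for early-censored patients. Scored as failures, they would lower the observed rate.
- *The follow-up rule contradicts intention-to-treat.* The patient stays in the analysis set. The plan leaves the outcome uncollected after new therapy and does not say how that therapy is handled, which is a gap and not a contradiction.
- *Pembrolizumab retreatment, also named in Section 7.1.5.5, hides events in the same way.* Section 5.5.2 links retreatment to relapse, which would come after the RFS event.

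**Conclusion.** The concern holds as a conditional one. It is plain from the text that recurrence status stops being collected at new anti-cancer therapy, and that nothing in the analysis plan deals with this. Direction and size are not established. Upward bias is the most plausible direction, because therapy without recorded recurrence may be started on suspicion of relapse. Under the assumptions above the size is about +1 to +5 points, with zero and about −1 to −2 points also possible. Against the planned difference of 60 − 32 = 28 points, the largest tabulated value, 4.8 points, is 17%. That would not by itself create the hoped-for effect, but it could matter for a result near the decision boundary, where one patient is worth about 4 points. The plan should be changed, because recurrence dates that are not collected may be hard to recover later.

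**What to change.** - **Data collection (Sections 1.0, 5.8, 6.1 footnote b, 7.1.1.5.3, 7.1.5.5 and 7.1.5.5.1).** After new anti-cancer therapy, continue to collect recurrence status, date and method until recurrence, death, withdrawal of consent, loss to follow-up or study end. Use the existing 12-weekly contact and routine-care imaging reports. No study-specific scan is needed and no treatment rule changes.
- **Main analysis (Section 8.2.2.1).** State that RFS is not censored at the start of new therapy.
- **Sensitivity analyses.** Report RFS censored at new therapy, and RFS with new therapy counted as an event.
- **Binomial test (Section 8.2.1).** State how patients censored before 12 months enter it.

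The cost is one extra data item for a few patients. Recurrence dates after new therapy will be less standardised than those from scheduled imaging. The main RFS estimate will include any effect of the new therapy, so it may move in either direction; the two sensitivity analyses show how far the result depends on that choice.

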5.9 Subject Replacement Strategy

No subject replacement strategy will be arranged.

5.10 Clinical Criteria for Early Trial Termination

Early trial termination will be the result of the criteria specified below:

1. Quality or quantity of data recording is inaccurate or incomplete
2. Poor adherence to protocol and regulatory requirements
3. Incidence or severity of adverse drug reaction in this or other studies indicates a potential health hazard to subjects
4. Plans to modify or discontinue the development of the study drug

In the event of Merck decision to no longer supply study drug, ample notification will be provided so that appropriate adjustments to subject treatment can be made.

6.0 TRIAL FLOW CHART

6.1 Study Flow Chart

Trial Period:	Screening Phase		Adjuvant Cisplatin-CRT		Pembrolizumab				End of Treatment	Post-Treatment		
Treatment Cycle/Title:	Pre-screening (Visit 1)	Main Study Screening (Visit 2)	1	2	To be repeated beyond 4 cycles				Discon	Safety Follow-up	Year-1 & Year-2	Year-3 & Year-4
					1	2	3	4				
Scheduling Window (Days):		-28 to -1	± 3	± 3		± 3	± 3	± 3	At time of Discon	30 days post discon	Every 3 months	Every 6 months
Pre-screening Consent	V											
Informed Consent		V										
Inclusion/Exclusion Criteria	V	V										
Demographics and Medical History		V										
Prior and Concomitant Medication Review		V										
Trial Treatment Administration ^a			V	V	V	V	V	V				
Survival Status ^b			V	V	V	V	V	V	V	V	V	V
Review Adverse Events ^c				V	V	V	V	V	V	V		
Full Physical Examination		V			V				V	V	V	V
Directed Physical Examination			V	V		V	V	V				
Vital Signs and Weight	V	V	V	V	V	V	V	V	V	V	V	V
ECOG Performance Status	V	V	V	V	V	V	V	V	V	V	V	V
Pregnancy Test – Urine or Serum β-HCG		V			V		V		V			
PT/INR and aPTT		V			V		V		V	V		
CBC with Differential		V	V	V	V	V	V	V	V	V	V	V
Comprehensive Serum Chemistry Panel ^d		V	V	V	V	V	V	V	V	V	V	V
Urinalysis		V			V		V		V	V		

Trial Period:	Screening Phase		Adjuvant Cisplatin-CRT		Pembrolizumab				End of Treatment	Post-Treatment		
	Pre-screening (Visit 1)	Main Study Screening (Visit 2)	1	2	To be repeated beyond 4 cycles					Safety Follow-up	Year-1 & Year-2	Year-3 & Year-4
Treatment Cycle/Title:					1	2	3	4				
Scheduling Window (Days):		-28 to -1	± 3	± 3		± 3	± 3	± 3	At time of Discon	30 days post discon	Every 3 months	Every 6 months
T3, FT4 and TSH		V			V		V		V	V	V	V
ACTH, Cortisol		V			V		V		V	V	V	V
Tumor Imaging ^e		V						V			V	V
Archival or Newly Obtained Tissue Collection ^f		V			V (optional)							
Correlative Studies Blood Collection (optional) ^g		V		V	V (every 4 cycles and recurrence)					V (Year-1 and 2: every 3 months until recurrence)		

^aTrial treatment may be administered up to 3 days before or after the scheduled Day 1 of each cycle due to administrative reasons.

^bOnce a subject experiences confirmed disease recurrence or starts a new anti-cancer therapy, the subject moves into the survival follow-up phase and should be contacted by telephone every 12 weeks to assess for survival status until death, withdrawal of consent, or the end of the study, whichever occurs first.

^cSAEs will be followed through 90 days following cessation of treatment, or 30 days following cessation of treatment if the subject initiates new anticancer therapy, whichever is earlier.

^dCheck bilirubin, AST, ALT, BUN, creatinine, Na, K, Ca, Mg, and other abnormalities found at screening check during adjuvant cisplatin-CRT phase; check bilirubin, AST, ALT, ALP, gamma-GT, LDH, albumin, BUN, creatinine, Na, Cl, K, Ca, Mg, P, glucose during pembrolizumab phase and post-treatment Year-1 to Year-4.

^eTumor imaging includes CT scan with/without contrast (if renal function is acceptable) for neck, chest, abdomen and symptomatic regions and esophagoscopy.

^fTissue proof for recurrent lesion if feasible.

^gBlood samples for biomarker study. The collection will be performed until disease recurrence (last blood sample collection).

7.0 TRIAL PROCEDURES

7.1 Trial Procedures

The Trial Flow Chart - Section 6.0 summarizes the trial procedures to be performed at each visit. Individual trial procedures are described in detail below. It may be necessary to perform these procedures at unscheduled time points if deemed clinically necessary by the investigator.

Furthermore, additional evaluations/testing may be deemed necessary by the Sponsor and/or Merck for reasons related to subject safety. In some cases, such evaluation/testing may be potentially sensitive in nature (e.g., HIV, Hepatitis C, etc.), and thus local regulations may require that additional informed consent be obtained from the subject. In these cases, such evaluations/testing will be performed in accordance with those regulations.

